### 7.2. Participant's characteristics

A table will present the baseline characteristics by condition group and overall. The table will include gender, age, ethnic group, proportion of students, highest educational qualification, years in higher education, equivalised household income, subjective socioeconomic position, BMI, dieting status, grocery shopping in supermarkets frequency, grocery shopping online frequency. Continuous variables will be summarised using means and standard deviations. Categorical variables will be summarised using counts and percentages.

### 7.3. Description of variables

#### Primary outcome

The main outcome variable is the **mean ED of the food items purchased** (kcal/100g) calculated as:

$$\text{Mean ED} = \frac{\sum_{i=1}^{10} \text{energy}_i}{\sum_{i=1}^{10} \text{weight}_i} \times 100$$

with *energy* in kcal, *weight* in g and *i* representing each food in the shopping list.

#### Secondary outcomes

#### **From the shopping task:**

- **Total energy** (kcal) of the foods purchased
- **Energy from total sugar** (% of total energy)
- **Energy from saturated fatty acids (SFA)** (% of total energy)
- **Salt content** (g/100g)
- **Proportion of lower ED foods** (as defined paragraph 5.1.) in the basket of foods purchased
- **Cost** (£, £/100g and £/100kcal) of the foods purchased

#### From the debriefing questionnaire:

- **Validity:** mean of item “*I would normally buy [the 10 items on the shopping list]*” for all the food items coded as: 1 = Never; 2 = Very rarely; 3 = Rarely; 4 = Occasionally; 5 = Frequently; 6 = Very frequently.
- **Kcal influence:** answer to the item “*The choices I made during online shopping were influenced by how many calories I thought were in the options available.*” coded as: 1 = Strongly disagree; 2 = Disagree; 3 = Slightly disagree; 4 = Neutral; 5 = Slightly agree; 6 = Agree; 7 = Strongly agree

#### Independent variables

##### **SEP**

#### **Level of education**

- **Highest educational qualification** will be coded from 1 to 9: 1 = No formal qualifications; 2 = 1–3 GCSEs; 3 = 4+ GCSEs; 4 = A level; 5 = Certificate of higher education (CertHE); 6 = Diploma of higher education (DipHE); 7 = Bachelor; 8 = Master’s degree; 9 = Doctorate, and as a binary variable as *lower* (values: 1, 2, 3, 4) or *higher* (values: 5, 6, 7, 8, 9).
- **Years in higher education**, as a continuous variable
- **Level of education (composite score):** In order to account for years in higher education and highest education qualification when characterising each participants’ education level, we will z-score the two variables and create an average of the two to form a composite score called ‘*level of education*’.

**Equivalent household disposable income:** The OECD-modified equivalence scale will be used to adjust household income, taking into account household size and composition [24]. Equivalent income will be calculated by dividing the after tax household income by the sum of the equivalence value of all the household members: first adult = 1, additional adult or child aged 14 and over = 0.5, child aged 0-13 = 0.3.

**Subjective SEP:** The measure of the Subjective Social Status using the MacArthur Scale will be coded from 1 to 10.

#### **Health and weight control food choice motives**

Both health and weight control scores will be computed by averaging ratings for individual items of each dimension (health motivation: 6 items; weight control motivation: 4 items). Response options range from 1 to 4: 1 = Not at all important; 2 = A little important; 3 = Moderately important; 4 = Very important. Cronbach’s alpha will be calculated as an indicator of internal consistency in order to compare our data with the original study that developed this measure [27].

#### Other variables

**BMI:** Self-reported height will be recalculated into height in metres (1 ft = 0.3048 m, 1 in = 0.0254 m). Self-reported weight will be recalculated into weight in kilograms. (1 stone = 6.35029 kg, 1 lb = 0.453592 kg). BMI will be calculated as weight (kg) / height (m^2). BMI data will be trimmed for implausible values excluding weight for less than 30 kg and more than 250 kg, height for less than 145 cm and more than 3m, BMI < 14 or BMI > 48 [30], [31].

**Aim guessing:** Participants who identify the aim of the study as being to examine the influence of labelling or increased proportion of lower ED/healthier food items on food purchases will be coded as being aware of the study aims. Responses will be independently coded by two researchers, with discrepancies in coding decisions resolved by a third researcher.

#### 7.4. Missing data

We do not anticipate missing data for analysis of the primary outcome for the population because ED is calculated based on the food database embedded in the online supermarket platform. We do not anticipate missing data either for the dependant variables because the questionnaires will not allow missing answers. Data from participants who start but not finish the study will not be included. Any *a posteriori* withdrawal will be reported and reasons for withdrawal will be documented (e.g., incorrect answers, technical problems).

#### 7.5. Primary analyses

The measure of SEP used in our primary analysis will be the *level of education* because previous research showed that people of higher education were more likely to use nutrition labels [32], [33].

**ANCOVA** will be used to test the effect of *labelling* (categorical variable: yes or no), *proportion* (categorical variable: default or increased), *level of education* (continuous variable) and *labelling\*level of education* and *proportion\*level of education* interactions on the *mean ED of foods purchased*. If this analysis reveals the predicted significant interaction between *labelling* or *proportion* condition and the continuous measure of *level of education* on *mean ED*, we will further examine the nature of the interactions by conducting floodlight analysis [34]. We will calculate the Johnson–Neyman point defined as the value of *educational level* for which the effect of *labelling* (or *proportion*) reaches statistical significance [35]. Values of *level of education* above this point will correspond to significant differences between the *labelling* and *no labelling* conditions (resp. the *default* and increased *proportion* conditions) whereas values below the point will not. The floodlight analysis will be run using the SAS macro developed by Hayes & Matthes, 2009 [36].

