### 4. PARTICIPANTS AND RECRUITMENT

#### 4.1. Recruitment

Participants will be recruited through an online recruitment panel (Prolific) in which participants are compensated proportionate to the time it takes to complete the online study ( $\approx$  £5/hour reward participants).

Participants' recruitment will be stratified by gender (50% male, 50% female), student status (3.5% yes and 96.5% no) [19] and qualification levels; the proportion of low (below level 4) versus high (level 4 or above) qualification levels will be based on current population statistics from the Labour Force Survey (LFS) 2013 for adults aged 19-64 in England [20]:

- **60% lower qualification levels**
  - No formal qualifications
  - 1–3 GCSEs or equivalent

*(Level 1: first certificate; GCSE - grades 3, 2, 1 or grades D, E, F, G; level 1 award; level 1 certificate; level 1 diploma; level 1 ESOL; level 1 essential skills; level 1 functional skills; level 1 national vocational qualification (NVQ); music grades 1, 2 and 3)*

- 4+ GCSEs or equivalent

*(Level 2: CSE - grade 1; GCSE - grades 9, 8, 7, 6, 5, 4 or grades A\*, A, B, C; intermediate apprenticeship; level 2 award; level 2 certificate; level 2 diploma; level 2 ESOL; level 2 essential skills; level 2 functional skills; level 2 national certificate; level 2 national diploma, level 2 NVQ; music grades 4 and 5; O level - grade A, B or C)*

- A level or equivalent

*(Level 3: A level; access to higher education diploma; advanced apprenticeship; applied general; AS level; international Baccalaureate diploma; level 3 award; level 3 certificate; level 3 diploma; level 3 ESOL; level 3 national certificate; level 3 national diploma; level 3 NVQ; music grades 6, 7 and 8; tech level)*

- **40% higher qualification levels**

- Certificate of higher education (CertHE) or equivalent

*(Level 4: certificate of higher education (CertHE); higher apprenticeship; higher national certificate (HNC); level 4 award; level 4 certificate; level 4 diploma; level 4 NVQ);*

- Diploma of higher education (DipHE) or equivalent

*(Level 5: diploma of higher education (DipHE); foundation degree; higher national diploma (HND); level 5 award; level 5 certificate; level 5 diploma; level 5 NVQ)*

- Bachelor or equivalent

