#### **7.8. Sample size**

##### To observe differences between the intervention groups and interaction with SEP

In a previous study (n=1,088) using the online supermarket platform, two types of nutritional interventions targeting a reduction of saturated fat (SFA) were compared: 1/ altering the default order of products in ascending order of SFA content 2/ offering explicit swaps with lower SFA [28]. This study showed a large main effect (f=0.42) of altering the default order: -4.78% (95%IC: -5.43 to -4.12) of energy from SFA; and a small-to-medium main effect (f=0.12) of offering swaps: -1.48% (95%IC: -2.19 to -0.76) of energy from SFA. Regarding ED reduction, this study showed a small-to-medium main effect (f=0.14) of altering the default order: -5.16 (95%IC: -7.3 to -3.02); and no significant main effect (f=0.04) of offering swaps -1.5 (95% IC: -3.65 to 0.67).

Based on these previous results, we will power our analyses to detect small main effects (f=0.1) of the *labelling* and *increased proportion* interventions. In an ANCOVA including four groups (*control*, *labelling*, *increased proportion*, *increased proportion & labelling*) and one covariate (*level of education*), to detect a main effect of *labelling* or *increased proportion* we will require a sample size of 788 participants (197 per group) for 80% power at  $\alpha = 0.05$  (GPower 3.1).

A sample size of 788 participants will allow to detect small interaction effects (f=0.1) of *labelling* or *increased proportion* with *level of education* in an ANCOVA including four groups (*control*, *labelling*, *increased proportion*, *increased proportion & labelling*) and one covariate (*level of education*) for 80% power at  $\alpha = 0.05$  (GPower 3.1).

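### The primary ANCOVA adjusts for education only, so precision that pre-randomisation age and gender could add to the intervention effects and their interactions with education may go unused

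*Combined protocol and SAP*

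**What the plan says.** Section 7.5 sets out one primary model. An ANCOVA "will be used to test the effect of" labelling, proportion, level of education, labelling by education and proportion by education on mean ED. Level of education is the only covariate.

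Nothing later in the plan adds another. Section 7.6 changes the analysed population or the education measure. Section 7.7 changes the outcome or adds the labelling-by-proportion interaction.

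Age and gender are items 1 and 2 of the baseline questionnaire (Appendix E). Section 6 places that questionnaire before randomisation, and Section 7.4 says the questionnaires will not accept blank answers. Their planned use is descriptive (Section 7.2): "The table will include gender, age, ethnic group, proportion of students, highest educational qualification" and further characteristics. Section 4.1 also says that "recruitment will be stratified by gender (50% male, 50% female", with student status and qualification level as further strata.

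On power, Section 7.8 states "we will require a sample size of 788 participants (197 per group) for 80% power at" alpha 0.05, for a main effect of f = 0.1 with four groups and one covariate. It adds: "A sample size of 788 participants will allow to detect small interaction effects (f=0.1) of" either intervention with education.

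**The concern.** The main hypothesis about socioeconomic position rests on an interaction, and the plan allows it 80% power at f = 0.1 in the smallest sample it expects to analyse. In a linear model, a baseline covariate that predicts the outcome lowers the residual variance, and so the standard error of every term, whether main effect or interaction. The plan already holds two such candidates, measured before allocation and without missing values, and leaves them out without giving a reason.

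What is at stake is some power, not validity. The choice has to be made in advance, because covariates picked after the data are seen invite suspicion of selection.

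**Working it through.** **Inputs.**
- From Section 7.8: f = 0.1 for main effects and for interactions, N = 788, four groups, one covariate, alpha 0.05, target power 80%.
- From Section 7.5: a primary model with 6 parameters (intercept, labelling, proportion, education, two interactions).
- Not in the documents: R², the share of the residual variance of mean ED, after the terms already in the model, that age and gender explain. I assume 0 to 10% and show the range.

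**Step 1: reproduce the plan's figure.** Power is the probability that a noncentral F variable with 1 and N − k degrees of freedom exceeds the 5% critical value, with noncentrality λ = f² × N. Here λ = 0.01 × 788 = 7.88.
- With k = 5 (four groups plus one covariate), the smallest N reaching 80% is 787, which becomes 788 for four equal groups (4 × 197). Power at 788 is 80.06%.
- With k = 6 (the model in Section 7.5), power at 788 is again 80.06%.

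The stated sample size is correct for the stated model.

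**Step 2: cost of adding covariates.** Age takes 1 parameter and gender with three categories takes 2, so k = 6 + 3 = 9 and the residual degrees of freedom go from 782 to 779. If the covariates explain nothing, power is still 80.06%.

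**Step 3: gain if they predict ED.** Adjustment multiplies the residual SD by √(1 − R²), so the effective effect size is f / √(1 − R²). The equivalent number of extra participants is 788 / (1 − R²) − 788.

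| Assumed R² | Effective f | λ | Power at 788 | Standard error falls by | Equivalent extra participants |
|---|---|---|---|---|---|
| 0 | 0.1000 | 7.88 | 80.1% | 0% | 0 |
| 2% | 0.1010 | 8.04 | 80.8% | 1.0% | 16 |
| 5% | 0.1026 | 8.29 | 82.0% | 2.5% | 41 |
| 10% | 0.1054 | 8.76 | 84.0% | 5.1% | 88 |

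**Step 4: does it hold for the interaction too?** A simulation of the Section 7.5 model used 4,000 trials of 788, with one added covariate that correlated 0.2 with education and had R² = 10%. Power went from 80.9% to 84.7% for the labelling main effect and from 79.1% to 83.2% for labelling by education. Both standard errors fell by about 5%, as in the table.

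**Step 5: how large might R² be?** The documents do not say. The nearest figure (Section 7.8) is r = −0.25 between healthiness motivation and kcal ordered in a virtual fast-food trial, or 0.25² ≈ 6% of variance. That is a different predictor, outcome and task, so it gives no estimate for age and gender.

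**The case against.** The strongest case against is that a lean, pre-specified model is legitimate, that the randomised comparisons need no adjustment, and that the benefit is unproven. No figure in the documents links age or gender to basket ED. With a fixed list of ten categories, ED may vary mostly through product choice within categories, so a low R² is plausible. All of this stands, and it limits the point to a worthwhile improvement.

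Nor is the plan's position on power precarious. 788 is a minimum: a loss of 20% from 1,000 leaves 800, where power is 80.6%. At the earlier ED effect of f = 0.14 for altering the default order, power at 788 is already 97.5%. At the f = 0.04 seen for swaps it is 20%, and R² = 5% would lift it only to 21%. Adjustment matters mainly for effects between these.

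A reader might infer more than the documents support, in four ways:
- *That adjustment removes confounding of education.* Education is not randomised, but the hypothesis about socioeconomic position concerns interactions, and covariate main effects do not remove confounding of an interaction. That would need intervention-by-covariate terms.
- *That the recruitment strata oblige adjustment.* Gender and student status are recruitment quotas in Section 4.1. Section 6 describes equal allocation to four groups and no stratified randomisation.
- *That dieting status belongs in the primary model.* Sections 2 and 7.7 hypothesise that health and weight-control motives help explain the education effect. Current dieting may lie on that pathway, so conditioning on it could remove part of what the trial wants to explain.
- *That student status should be added.* At 3.5% of the sample (0.035 × 788 ≈ 28 people) it can explain little. It is also tied to the education measure, because students report the qualification they are studying for (Appendix E, item 5).

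**Conclusion.** The point holds as a missed efficiency. Section 7.5 leaves out two covariates that are measured before randomisation, complete by design and almost free to include. The plan is neither wrong nor biased without them, and 788 is right for the model as written.

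Over the assumed R² of 2% to 10%, the gain at f = 0.1 is about 1 to 4 percentage points of power, for main and interaction effects alike. It is nil if age and gender do not predict ED. The conclusion that adjustment costs essentially nothing does not depend on R²; the size of the benefit depends on it entirely. The calculation assumes a linear covariate effect, a common residual variance and f defined on the residual SD of the current model.

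**What to change.** In Section 7.5, pre-specify age (continuous) and gender (categorical) as covariates in the primary ANCOVA and carry them into its repeats in Sections 7.6 and 7.7. State how participants who choose Other for gender are handled. Say that the adjusted model is the one used for inference, and report the model without age and gender alongside. For consistency, state whether the same two covariates enter the moderated mediation model.

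Leave student status out, and use dieting status in a sensitivity analysis at most. The motive scores should not serve as adjusters, because Section 6 places them after the shopping task.

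The cost is a few sentences of plan text and three model parameters. It needs no new data, no extra participants and no change to the sample size.

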## 1. BACKGROUND AND RATIONALE

People of lower socioeconomic position (SEP) are more likely to have obesity than people of higher SEP and SEP inequities in obesity in Europe are widening [1]. Lower socioeconomic position (SEP) is associated with a more energy dense diet [2], [3]. Consumption of more energy dense foods has been consistently linked to higher energy intake in experimental studies [4] and results from prospective cohort studies have shown a positive association between energy density (ED) of the total diet and BMI [4]. Thus, the association between SEP and obesity may be mediated, in part, by the consumption of a more energy-dense diet [5]. Interventions that reduce dietary energy density would benefit public health, particularly among people of lower SEP.

In the UK, 26% of the adults eat meals out one or more times per week and 20% eat takeaway meals at home one or more times per week, suggesting that the major part of the meals consists in food prepared at home [6]. People from lower SEP tend to spend a greater proportion of their average food expenditure on prepared-at-home produce (such as products purchased in supermarkets) as opposed to catering services than people of higher SEP (lowest equivalised disposable income decile group: 74% vs. highest: 60%) [7]. Thus, nutrition interventions targeting supermarket purchases provide an opportunity to benefit the diet of all of the population and people of lower SEP in particular.

Information-based nutrition interventions are one of the most common approaches to improving diet [8], [9]. An example of an information-based intervention is menu energy labelling in restaurants [10]. This type of interventions has been suggested to be less effective among people of lower compared to higher SEP [11], [12]. However, systematic reviews of the impact of menu energy labelling has highlighted the limited quality of evidence supporting this hypothesis [11], [13]. It has been suggested that structural interventions that target core features of the food environment (i.e., reducing portion sizes, increasing the availability of healthier food options) and require individuals to use a low level of agency may be most effective and most equitable [8], [14], [15]. However, there is a lack of empirical evidence to support this hypothesis.

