## 2. OBJECTIVES, OUTCOMES MEASURES AND HYPOTHESES

OBJECTIVES	OUTCOME MEASURES	HYPOTHESES
Primary objective		

To examine the effectiveness of an information-based intervention (ED labelling) and a structural nutrition intervention (greater proportion of lower ED options) on the ED of virtual online supermarket food purchases; and if this effect is different between participants of lower and higher SEP.	Mean ED (kcal/100g) of foods purchased	SEP will influence the effect of the interventions. In particular, ED labelling will reduce ED of foods purchased to a greater extent in participants of higher vs. lower SEP. Conversely, a greater proportion of lower ED options will decrease ED of food purchases equally among participants of lower and higher SEP.
Secondary objectives  To investigate the psychological processes that explain why an information-based intervention (ED labelling) and a structural nutrition intervention (greater proportion of lower ED options) may have differential effects on ED of food purchases among participants of lower vs. higher SEP.	Health and weight control food choices motives (questionnaire score)	The participants of higher SEP will be more motivated by health and weight control in their food choices than participants of lower SEP, which will moderate the relationship between SEP and the effect of ED labelling on ED of foods purchased.

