## 7. STATISTICAL ANALYSIS

All statistical analyses will be performed using SAS version 9.3 (SAS Institute, Inc., 2012 SAS® 9.3. Cary, NC). The level of significance will be set at  $p < 0.05$  for primary and sensitivity analyses and at  $p < 0.01$  for secondary analyses.

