## **APPENDIX I: DEBRIEFING TEXT**

*“In this study we were interested in the effect of nutrition interventions on online grocery shopping. You have seen one version of the online supermarket but other participants have seen different ones. The difference between the four versions of the online supermarket is the food items they offer. In the first version, the food offer reflects what you can find in an online supermarket in the UK; in the second one low-energy badges are added to indicate the options with fewer calories per gram within a food category.; in the third one the proportion of lower-energy food items is increased; in the fourth one low-energy badges are added and the proportion of lower-energy food items is increased. We will compare the energy per 100g of the foods purchased by the participants from the four versions of the online supermarket. The results will help to identify the most promising intervention to reduce the overall energy of our diets.”*

*“Thank you very much for your participation in our study!”*

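### The hypotheses contrast labelling and increased proportion on how far each effect depends on education, but no planned analysis compares the two interactions

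*Combined protocol and SAP*

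**What the plan says.** Section 2 (and the aim at the end of section 1) makes two predictions. Labelling will lower energy density (ED) more in participants of higher SEP. The second prediction is set against the first: "Conversely, a greater proportion of lower ED options will decrease ED of food purchases equally among participants of lower and higher SEP".

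Section 7.5 fits one ANCOVA with labelling, proportion, level of education and "labelling\*level of education* and *proportion\*level of education* interactions on the *mean ED of foods purchased". An interaction that is significant on its own is followed up by floodlight analysis. Under section 7.7 a significant interaction also leads to the moderated mediation analysis. Section 7 sets the threshold: "The level of significance will be set at $p < 0.05$ for primary and sensitivity analyses".

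The only planned term that involves both interventions is the labelling-by-proportion interaction, added in a repeat of the primary analysis in section 7.7.

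Section 7.8 sizes the trial for each effect separately: "we will require a sample size of 788 participants (197 per group) for 80% power" for a main effect, and "A sample size of 788 participants will allow to detect small interaction effects (f=0.1") for either factor with education.

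**The concern.** The second prediction is worded as the opposite of the first, so a reader of the results will want to know whether the two interventions differ in their dependence on education. As planned, the report will hold two separate p-values. If labelling-by-education falls below 0.05 and proportion-by-education does not, the natural sentence is that labelling acts unequally across SEP whereas increased proportion does not. That sentence contains a comparison, and two separate tests against zero do not test it: one estimate can be significant and the other not while the two are close together. The labelling-by-proportion term does not fill the gap. It asks whether the two effects add up, not which of them varies more with education.

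At stake is a statement about relative equity with neither a controlled error rate nor an interval. This is separate from whether equality across SEP can be shown for increased proportion alone. An equivalence result for that intervention would still not compare it with labelling.

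**Working it through.** **Inputs.** Alpha 0.05 (section 7); analysed N = 788, 197 per group, and f = 0.1 for each main effect and each interaction (section 7.8); equal allocation to four groups (section 6).

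**1. Reproducing the plan's figure.** For a 1-df F test with four groups and one covariate, the denominator df are N − 4 − 1 and the noncentrality is λ = N·f². The smallest N for 80% power at f = 0.1 is 787, or 788 in four equal groups. At 788, λ = 788 × 0.01 = 7.88 and power is 80.1%. The plan's number is confirmed.

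**2. Chance of the predicted pattern when the two interactions are equal.** In a balanced 2×2 the two interaction estimates are essentially uncorrelated with equal variance. If each has power p, then P(labelling significant, proportion not) = p(1 − p), and discordance in either direction has probability 2p(1 − p).

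| Common f | Power p | p(1 − p) | 2p(1 − p) |
|---|---|---|---|
| 0.05 | 0.289 | 0.205 | 0.411 |
| 0.07 | 0.501 | 0.250 | 0.500 |
| 0.10 | 0.801 | 0.160 | 0.319 |
| 0.12 | 0.920 | 0.074 | 0.147 |
| 0.14 | 0.975 | 0.024 | 0.048 |

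The f = 0.07 row is the worst case, because p(1 − p) peaks at p = 0.5. With no interaction for either intervention the figure is 0.05 × 0.95 = 4.8%.

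Simulation of the section 7.5 model (6,000 runs per scenario) gave 15.7% for the predicted pattern at f = 0.1 and 24.9% at f = 0.07. The direct contrast rejected in 5.0% and 5.2% of runs.

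**3. One illustrative result.** Take z = 2.8 for labelling-by-education and z = 1.0 for proportion-by-education. The first is significant and the second is not. The difference has z = (2.8 − 1.0)/√2 = 1.27, p = 0.20.

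**4. Power of the direct contrast.** The variance of the difference is twice that of one coefficient, so λ = N·(f_L − f_P)²/2, where L is labelling and P is proportion.

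- f = 0.1 against 0: λ = 788 × 0.01/2 = 3.94; power 50.9% (simulation 50.3%). About 1,572 analysed would be needed for 80%.
- f = 0.1 against 0.05: λ = 788 × 0.0025/2 = 0.985; power 16.8%. About 6,280 would be needed for 80%.

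**5. When the hypothesis is exactly true** (0.1 and 0), the predicted pattern appears in 0.801 × 0.95 = 76% of trials. In simulation, the pattern together with a significant contrast appeared in 46.5%.

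**The case against.** The strongest reply is that the trial does not set out to rank the interventions. The primary objective asks whether each one affects ED and whether that effect differs by SEP, and the two hypotheses can be read as separate statements. Labelling-by-education tests the first directly. That stands, and so does the sample size for the tests it serves.

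A reader might go further and infer that the trial's central conclusion is a head-to-head comparison left untested, including which intervention is more effective. The documents do not support that. The phrase in section 1 about structural measures that "require individuals to use a low level of agency may be most effective and most equitable" reports a suggestion from the literature. "The results will help to identify the most promising intervention to reduce the overall energy of our diets" comes from the lay debriefing text in Appendix I. Neither is an objective, and no hypothesis says which intervention lowers ED more. Nor does the plan state a rule that infers a difference from discordant p-values. Significance in section 7.5 decides whether to run the follow-up analysis, and section 7.6 compares sensitivity analyses with the main analysis.

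It is also fair to say that the 16% is simply 0.80 × 0.20, a true interaction found and another missed, and that it shrinks quickly once both interactions are larger than f = 0.1. Finally, the direct contrast is itself weak at 788.

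What remains is narrower. The hypotheses in sections 1 and 2 do oppose the two interventions on SEP dependence, and the plan offers no estimate of that difference and no caution against reading it from two p-values.

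**Conclusion.** The point holds as a low-cost improvement confined to the interaction comparison. Any statement that the two interventions differ in how far their effect depends on education is untested as planned. With truly equal interactions at the design value f = 0.1, the predicted split in significance arises in about 16% of trials. Between f = 0.05 and f = 0.14 the figure ranges from 25% (near 0.07) down to about 2%.

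It does not follow that the primary tests or the 788 are wrong, or that the trial has left an effectiveness ranking untested, since it never set one as a hypothesis.

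The figures assume equal groups after exclusions, education independent of allocation, normal errors with constant variance, no labelling-by-proportion interaction, and effects of the two factors on the same f scale.

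**What to change.** - **Section 7.5:** code both factors as intervention minus no intervention. From the same ANCOVA, add one supportive contrast, labelling-by-education minus proportion-by-education, reported with a 95% confidence interval. State that any claim that one intervention is more or less equitable than the other rests on this contrast, not on one interaction being significant and the other not.
- **Section 7.8:** state that at 788 the contrast has about 51% power for f = 0.1 against 0 and about 17% for f = 0.1 against 0.05, so it will mainly serve as an estimate with its interval.
- **Optional:** a labelling-minus-proportion contrast of main effects, labelled descriptive, and needed only if the report will rank the interventions on effectiveness.

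The cost is one estimate statement on a model already fitted and a few sentences. Existing tests, alpha and sample size are unchanged, and no new data are needed. The real downside is that the comparative equity claim becomes harder to make: even if the hypothesis is exactly true at f = 0.1 against 0, the contrast will miss it about half the time.
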